7.6 Drug accountability

A Drug Accountability form will be used to record IMP dispensing and return information on a by-subject basis and will serve as source documentation during the course of the study. Details of any IMP lost (due to breakage or wastage), not used, disposed of at the study site, or returned to the Sponsor or designee must also be recorded on the appropriate forms. All supplies and pharmacy documentation must be made available throughout the study for UCB (or designee) to review.

The Investigator (or designee) is responsible for retaining all used, unused, and partially used containers of IMP until return or destruction.

The Investigator may assign some of the Investigator's duties for drug accountability at the study site to an appropriate pharmacist/designee.

The Investigator must ensure that the IMP is used only in accordance with the protocol.

Procedures for monitoring subject compliance 7.7

At each on-site visit after IMP is dispensed, subjects must return all used and unused IMP to the site.

missed due to a reasonable interfering AE that does not alk auministration of an anti-TNF due to safety reasons will not be considered for the exposition of subject compliance. Evaluation of the reasonability of the AE must be discussed immediately with the Medical Monitor. Doses of IMP that were missed due to a reasonable interfering AE that does not allow administration of an anti-TNF due to safety reasons will not be considered for the evaluation

7.8 Concomitant medication(s)/treatment(s)

7.8.1 Permitted concomitant treatments (medications and therapies)

The following concomitant medications are permitted during the study for uveitis:

- Corticosteroids (see Section 7.8.2 for prohibited corticosteroids): Oral chronic stable doses are allowed as long as the maximum daily total prednisone equivalent dose is ≤10mg (see Table 6–1).
 - Oral corticosteroid tapers of less than 14 days used to treat other indications (asthma exacerbation, contact dermatitis, etc) are allowed as long the maximum daily dose is ≤20mg. The taper must end 1 week before a study visit.

The following concomitant medications are permitted during the study for axSpA:

- NSAIDs/cyclooxygenase 2 (COX-2) inhibitors
 - Stable doses of analgesics established at Baseline (including, but not limited to acetaminophen, paracetamol, NSAIDs, opiates or combinations) will be permitted except that ad hoc (prn) usage is prohibited within the 14 days prior to Baseline or 24 hours prior to any post-Screening assessments.
- Corticosteroids (see Section 7.8.2 for prohibited corticosteroids): Oral chronic stable doses are allowed as long as the maximum daily total prednisone equivalent dose is ≤10mg (see Table 6–1).
 - Oral corticosteroid tapers of less than 14 days used to treat other indications (asthma exacerbation, contact dermatitis, etc) are allowed as long the maximum daily dose is ≤20mg. The taper must end 1 week before a study visit.
 - Intra-articular (ia) administration of corticosteroids is permissible in peripheral joints; however, after an ia injection the joint will no longer be evaluated for data regarding swollen and tender joints.
 - Intravenous (iv) administration of corticosteroid will be permitted for the purposes of stress dosing for a surgical procedure under general or spinal anesthesia. Furthermore, iv administration of corticosteroids may be used during the study for acute illnesses as long as the dose is not given within 1 week prior to Week 12, Week 24, Week 48, or Week 96, and the underlying disease does not present a contraindication to the subject remaining in the study. Indications might include dermatitis, gastroenteritis, asthma exacerbation, and pneumonia.
- Disease-modifying antirheumatic drugs (DMARDs) (only SSZ and/or hydroxychloroquine [HCQ] and/or MTX and/or azathioprine [AZA] and/or leflunomide [LFN]: maximum SSZ ≤3g daily; HCQ ≤400mg daily; MTX ≤25mg weekly; AZA ≤150mg daily; LFN ≤20mg daily) are allowed. No change in dose or dose regimen is allowed during the study except for reasons of intolerance, where the DMARDs dose may be reduced or discontinued. No change is permitted in the route of administration for MTX (sc or oral) during the study.

Osteoporosis medications (eg., risedronate, alendronate, ibandronate, denosumab, cathepsin K inhibitor, cinacalcet, calcitonin) with the exception of iv bisphosphonates are allowed without restriction.

7.8.2 **Prohibited concomitant treatments (medications and therapies)**

Variations thereof. Prior medication exclusions and washout periods are listed in Section 6.2. In addition, use of the following concomitant medications is prohibited during the study, except where indicated:

- Corticosteroids (administered oral, ia, or iv) are permitted only as described in Section 7.8.1. Intramuscular corticosteroids and SIJ ia corticosteroid injections are not permitted.
- Hyaluronic acid may be used as in injection in the knee only.
- Specific DMARDs (cyclosporine, cyclophosphamide, mycophenolic acid, apremilast). Biologicals (TNF antagonists: IFX, ADA, ETN, GOL; abatacept [ABA]; CZP; Rituximab or other anticluster of differentiation 20 [anti-CD20] antibodies; tocilizumab; ustekimumab; tofacitinib; or any other biological response modifiers that are not licensed for the treatment of AS or axSpA).
- All iv bisphosphonates (zoledronic acid, ibandronate, pamidronate) are excluded.
- Subjects must not participate in any other clinical study for any indication or receive any unauthorized medication during the Study Period.

If the subject requires any of the medications specified in this section, the subject must be withdrawn from the study prior to the initiation of these medications.

The administration of live vaccines is not recommended for subjects treated with TNF antagonists. Live vaccines should not be administered 8 weeks prior to Baseline. If immunization with a live organism-based vaccine is considered during the study, the clinician is urged to carefully weigh the risks vs benefits of immunization. If the subject is going to proceed with live organism-based immunization, the subject must be withdrawn from the study prior to administration of the vaccine. Such vaccines must be recorded in the electronic Case Report Form (eCRF).

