8.2.6 Swollen and tender joint counts

The following 44 joints are to be examined for swelling and tenderness by the Investigator, another delegated physician, or an appropriately qualified medical professional (based on local requirements) who has had documented training on how to perform these assessments correctly. Preferably the same assessor should evaluate the subject at each arthritis assessment.

- Upper body (4) – bilateral sternoclavicular and acromioclavicular joints.
- Upper extremity (26) – bilateral shoulders, elbows, wrists (includes radiocarpal, carpal, and carpometacarpal bones considered as a single unit), metacarpophalangeals (MCPs) I, II, III, IV, and V, and thumb interphalangeals (IPs), and proximal IPs (PIPs) II, III, IV, and V.
- Lower extremity (14) – bilateral knees, ankles, and metatarsophalangeals (I, II, III, IV, and V).

The assessment for swelling and tenderness is made on 44 joints from the above list. Artificial, ankylosed, and missing joints are excluded from swelling and tenderness assessments.

Each joint is scored for tenderness as follows:

0 = None (not tender)

1 = Positive (tender)

Each joint is scored for swelling as follows:

0 = None

1 = Detectable

Tender joint counts (TJC) and swollen joint counts (SJC) are calculated as the sum of tender and swollen joints, respectively, among the 44 joints. Both TJC and SJC range from 0 to 44.

If there are missing observations for tender or swollen joints then the remaining observations will be assessed and weighted by dividing by number of non-missing and then multiplying by 44 for the joint count. If a joint is not evaluable at Baseline, then that joint is set to missing throughout the study. If data for more than 50% of the joints are missing at the time of a given assessment, then no imputation will be done and the total TJC or SJC will be set to missing for that visit.

TJC summaries will be based only on those subjects with at least one tender joint at Baseline. Similarly, SJC tables will be based only on those subjects with at least one swollen joint at Baseline.

The data including the change from baseline at Week 48 and Week 96 will be summarized as secondary endpoints.

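### Joints given a permitted intra-articular steroid injection drop out of the tender and swollen joint counts, which shifts the recorded change in favour of CZP

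*Protocol*

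**What the plan says.** Protocol 7.8.1 permits ia corticosteroid in peripheral joints while the subject is on study, with the consequence that "after an ia injection the joint will no longer be evaluated for data regarding swollen and tender joints". No end to that exclusion is given.

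SAP 8.2.6 defines the tender joint count (TJC) and swollen joint count (SJC) as sums of 0/1 scores over 44 joints. It does not mention injected joints. Four of its rules bear on them:

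- "Artificial, ankylosed, and missing joints are excluded from swelling and tenderness assessments".
- Where observations are missing, "the remaining observations will be assessed and weighted by dividing by number of non-missing and then multiplying by 44 for the joint count".
- Any joint that could not be scored at the Baseline visit counts as missing from then on. There is no matching rule for a joint lost after Baseline.
- The total is left missing only "If data for more than 50% of the joints are missing at the time of a given assessment", so one or a few injected joints never trigger this.

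The TJC and SJC tables are restricted to subjects with at least one tender or swollen joint at Baseline, respectively. Change from Baseline in both counts at Weeks 48 and 96 is a secondary efficacy variable (SAP 2.2.1.2). SAP 4.2 specifies observed-case analysis.

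**The concern.** The Baseline rule protects a like-for-like comparison in one direction only. A joint that cannot be assessed at Baseline is removed from every visit. A joint that is positive at Baseline and later injected is counted at Baseline and absent afterwards. Because injection is prompted by activity, the joints that disappear are mainly positive ones, and what remains is a less affected set.

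For these two variables, a joint that needed local steroid despite CZP is therefore either recorded as improved or has its deterioration left out. Both errors favour CZP. The study has one arm, so no comparator group carries the same distortion and allows it to cancel.

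**Working it through.** **The denominator.** The joint list in SAP 8.2.6 gives 4 upper-body joints, 2 × (1+1+1+5+1+4) = 26 upper-extremity joints and 2 × (1+1+5) = 14 lower-extremity joints. The total is 4 + 26 + 14 = 44, which matches the plan.

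**Case 1: a Baseline-positive joint is injected and nothing else changes.** Let k be the positive count at Baseline with all 44 joints assessed. One positive joint leaves the numerator and the denominator falls to 43.

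- Recorded count = (k-1) × 44/43
- Recorded change = (k-1) × 44/43 - k = -(44-k)/43
- Change if the joint were dropped without proration = -1
- True change, by construction of this case = 0

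| k at Baseline | Recorded later | Recorded change | Relative change |
|---|---|---|---|
| 1 | 0 | -1.00 | -100% |
| 2 | 1.02 | -0.98 | -48.8% |
| 3 | 2.05 | -0.95 | -31.8% |
| 5 | 4.09 | -0.91 | -18.1% |
| 10 | 9.21 | -0.79 | -7.9% |

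The change is negative for every k below 44. Comparing it with -1 shows that dropping the joint causes the shift and that proration gives a little back.

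**Case 2: two Baseline-positive joints are injected.** With k = 3, the recorded count is (3-2) × 44/42 = 1.05, a change of -1.95.

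**Case 3: a joint negative at Baseline becomes active and is injected.** The true count is k+1 and the recorded count is k × 44/43. With k = 3, this is 3.07 against a true 4. The recorded change is +0.07 instead of +1, so the worsening is lost but no improvement is shown.

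**Group level.** The documents give no injection rate. Purely as an assumption, suppose 5% to 20% of subjects in the table have one Baseline-positive joint injected. The mean shift is that proportion times -(44-k)/43: about -0.05 to -0.20 joints if every subject has k = 1, and about -0.05 to -0.19 if every subject has k = 3.

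**The case against.** Several objections carry weight. SAP 8.2.6 never says that an injected joint is missing; that is an inference from the protocol's instruction to stop evaluating it. It stands as the natural reading, because no other SAP rule fits and none contradicts it.

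A reader might infer that proration creates the false improvement, or that every injected joint is scored as a success. Neither follows. Proration moves the count up slightly (1.02 rather than 1.00 at k = 2), and Case 3 shows that an injected joint that was negative at Baseline produces no recorded improvement.

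The large percentages describe single hypothetical subjects with low counts. Nothing in the documents shows how many subjects would be affected. Concomitant medications are also listed with route and indication (SAP 6.4), so ia steroid use should already be visible by subject. That helps a reader notice the problem but does not correct the counts.

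The obvious remedy, freezing the last pre-injection score, has its own weakness. Joint counts are scheduled at set visits (SAP Table 2-1) and are not among the unscheduled-visit assessments in Protocol 8.8. A joint that flared and was injected between visits could be held at 0 for the rest of the study. The fix has to allow for this.

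**Conclusion.** The concern holds as a minor point. Followed as written, the two documents bias change from Baseline in TJC and SJC towards CZP. The bias is (44-k)/43 joints per subject when one Baseline-positive joint is injected and nothing else changes. When the injected joint is newly active, nearly all of the one-joint worsening is erased.

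This rests on three assumptions: joints are injected because they are active; the injected joint is one of the 44; and a joint no longer evaluated is handled as missing.

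It would be wrong to infer that the trial's main conclusion is at risk. The AU flare analysis, ASDAS, BASDAI and ASAS responses do not use the joint counts. SAP 8.2 summarises the counts descriptively, and SAP section 8 makes everything except the primary analysis exploratory. The overall size cannot be stated without the number of injections.

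**What to change.** In SAP 8.2.6, add a rule for post-Baseline ia corticosteroid injection, applied separately to tenderness and swelling:

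- The joint is not treated as missing. It is scored 1 at all later visits if it was positive at Baseline, at the last assessment before injection, or according to the recorded reason for injection.
- The rule is stated to be an exception to the observed-case approach in SAP 4.2.
- The count under the current proration rule is shown alongside as a sensitivity summary.
- The numbers of subjects and joints injected by Weeks 48 and 96 are reported.

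In Case 1 the recorded change becomes 0 for every k. In Case 3 with k = 3 the recorded count becomes 4, provided that the last assessment or the recorded reason identifies the joint as active. The permission in Protocol 7.8.1 is left as it is.

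The cost is a short SAP paragraph, one extra summary and a flag for the injected joint. The medication fields listed in SAP 6.4 do not include joint location, so the flag must come from the joint-assessment records or from further detail in the medication records. The rule also overstates activity if the joint would have settled anyway, which is why the prorated version should be kept for comparison.

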7.8.3 Rescue medication

A rescue medication is any medication other than prohibited medication that is used to treat axSpA or weitis. The use of rescue medication is allowed during Screening through Week 96/WD Visit, except under the conditions noted in Section 7.8.2.

Enrollment into treatment and numbering of subjects

Blinding

Blinding

This will be an open-label study; therefore, blinding is not applicable.

7.10 Enrollment into treatment and process.

An IWRS will be used for An IWRS will be used for assigning CZP treatment to eligible subjects. The IWRS will generate individual assignments for subject kits of IMP, as appropriate, according to the visit schedule.

To enroll a subject into the study (Visit 1), the Investigator or designee will contact the IWRS and provide brief details about the subject to be enrolled. Each subject will receive a ... and investigator or conject numbers and kit numbers will

... subject into the Treatment Phase, the Investigator or designee will contact the IWRS and provide brief details about the subject to be enrolled. The IWRS will automatically allocate kit numbers to the subject based on the subject number during the course of the study.

8 STUDY PROCEDURES BY VISIT

Section 5.2 (Schedule of assessment) letailed listing of 5-digit number assigned at Screening that serves as the subject identifier throughout the

detailed listing of procedures to be undertaken at each visit is described below. During the study, the Investigator will assess each subject over the entire study period of up to 109 weeks including a FU Period of 10 weeks after the last dose of the study drug. For Week 2 to Week 96 the visit window is ± 3 days from the actual date in Weeks from the initial administration of IMP (Week 0). For the FU Visit a window of 1-2 weeks is acceptable.

Visit 1 (Week -5 to -1) Screening 8.1

Prior to any study activities, subjects will be asked to read and sign an informed consent form (ICF) for participation in the study. All ICFs will have been approved by an IEC/IRB and will comply with regulatory requirements. Subjects will be given adequate time to consider any information concerning the study given to them by the Investigator or designee. As part of the informed consent procedure, subjects will be given the opportunity to ask the Investigator any questions regarding potential risks and benefits of participation in the study.

Assessments at the Screening Visit include:

- Confirm informed consent
- Review inclusion/exclusion criteria
- Demographic data (includes date of birth, gender, race/ethnicity)
- Washout of excluded medications (3 months for TNFs)
- Significant past medical and procedure history (including tobacco use) and concomitant disease (including axSpA history)
- Prior and concomitant medication
- Review of the uveitis history containing all documented UA
- Vital signs (pulse rate, systolic and diastolic blood pressures, and temperature)
- Physical examination (including weight) and extra-articular assessment (including the number of IBD exacerbations and number of psoriasis exacerbations [in subjects with concurrent psoriasis])

- Hematology, biochemistry, and urinalysis for clinical laboratory values
- Hepatitis-associated disease markers assessment:
 - Hepatitis B core antibody (HBc-Ab)
 - Hepatitis B surface antigen (HBs-Ag)
 - Hepatitis B surface antibody (HBs-Ab)
 - Hepatitis C virus antibody (HCV-Ab)
- Testing of antibodies to HIV
- Testing for HLA-B27 if unknown at Screening Visit
- CRP testing
- Serum pregnancy testing for women of childbearing potential
- TB evaluation
- nd any extensions of variations thereof. Screening chest x-ray must have occurred within 3 months prior to Screening and should be repeated only if the TB test was confirmed positive or any further evidence is suggestive of potential TB infection (eg, exposure).
 - TB: IGRA test (QuantiFERON TB GOLD test).
 - TB evaluation questionnaire (includes evaluation of signs and symptoms of active TB and risk factors for exposure to TBY
- Chest x-ray used for screening must have been done within 3 months prior to the Screening Visit and should be repeated only if the TB test was confirmed positive or any further evidence is suggestive of potential TB infection (eg, exposure). If no chest x-ray is available within the 3 months prior to the Screening Visit, the x-ray can be done during the Screening Period.
- For subjects with nr-axSpA, an MRI of the SIJs is to be performed during the Screening Period. An MRI performed ≤3 months prior to the Baseline Visit may be used as the Baseline. An MRP assessment is not needed for patients with AS.
- AS subjects must have evidence of sacroiliitis on x-ray taken prior to Baseline meeting the mNY classification criteria according to the Investigator. If not available, this x-ray is to be taken during the Screening Period. If an x-ray was performed prior to the Screening Visit and the mNY classification criteria were met, the x-ray is not to be repeated.
- BASDAI
- Contact the IWRS to indicate the subject has been screened
- Schedule appointment for next visit

The Screening chest x-ray should be read by an experienced TB imaging specialist, radiologist, pulmonologist or infectious disease specialist, who is specifically requested to look for signs of active TB or signs of past/inactive TB infection and must exclude evidence of TB. For subjects with LTBI who initiate a prophylactic treatment and need to have

8 weeks of prophylactic treatment prior to randomization, the Screening Period can be extended to 12 weeks. For other subjects, the Screening Period should be kept as short as possible, but can be up to 5 weeks if certain medications need to be washed out or to allow to obtain information from the subjects' ophthalmologist.

8.2 Visit 2 (Week 0) Baseline Visit

Subjects qualifying for the study will have the following procedures performed/recorded prior to study medication administration:

- Review of inclusion/exclusion criteria
- Evaluation of uveitis flares that occurred since last visit
- Prior and concomitant medications
- Vital signs (pulse rate, systolic and diastolic blood pressure, and temperature)
- Physical examination and extra-articular assessment
- Physical examination and extra-articular assessment

 Height

 Weight

 Number of IBD exacerbations

 Number of psoriasis exacerbations (in subjects with concurrent psoriasis)
- Blood samples will be collected for
 - Hematology analyses
 - Biochemistry analyses
 - CRP testing
- Urine will be collected for
 - Urinalysis
 - Urine pregnancy test for women of childbearing potential
- TB questionnaire
- Patient reported outcomes:
 - BAŠDAI

BASFI

- **ASQoL**
- ASAS HI questionnaire
- SF-36
- Total and nocturnal spinal pain
- **PtGADA**

- **PhGADA**
- Swollen and tender joint counts

- . since last visit

 . since last visit

 . swill be collected for
 . natology analyses

 CRP testing

 Urine will be collected for urinarysis

 Patient reported outcomes:

 BASDAI

 BASFI

 ASQOL

 ASAS HI

 F-2

8.3

Assessments at these visits will include:

- - ASAS HI questionnaire
 - SF-360
 - Total and nocturnal spinal pain

PtGADA

PhGADA

- Swollen and tender joint counts
- Contact IWRS to obtain kit numbers

AEs

- Study drug administration on-site. At Week 4, syringes of CZP are provided for home administration at Weeks 6, 8, and 10. The subject has to return 1 syringe at the Week 12 Visit.
- Schedule appointment for next visit

8.4 Visits 5 and 6, and Visits 8 to 12 (Weeks 12, 24, 36, 48, 60, 72, and 84)

Assessments at these visits will include:

- Evaluation of uveitis flares that occurred since last visit
- Concomitant medications
- Vital signs (systolic and diastolic blood pressures)
- Physical examination (weight at Week 48 only) and extra-articular assessment (including the number of IBD exacerbations and number of psoriasis exacerbations [in subjects with concurrent psoriasis])

 Blood samples will be collected for

 Hematology analyses

 Biochemistry analyses

 CRP testing

 Urine will be collected for urinalysis

 TB test for subjects with previously negative TB test result (Week 48 only)

- TB questionnaire
- Patient reported outcomes:
 - **BASDAI**
 - **BASFI**
 - **ASQoL**
 - ASAS HI questionnaire

Total and nocturnal spinal pain

PtGADA

- **PhGADA**
- Swollen and tender joint counts
- **AEs**
- Contact IWRS to obtain CZP kit numbers
- Study drug administration onsite

- Provide subject with CZP for home administration Q2W until next scheduled site visit
- Schedule appointment for next visit

